Here we propose to quantify the effect of the HWA on walking at the knee, ankle, trunk and arm segments during phases of the gait cycle (GC) as described by Perry. (Perry & Davids, 1992) Additionally, we will quantify the aftereffect of HWA use in these joints and segments. Quantification will include measurement of walking kinematics (joint angles), muscle activity (EMG output), ground reaction forces and Spatiotemporal gait characteristics measured in three conditions: 1) Walking at self-selected pace (control), 2) walking with the HWA (4Nm assist), 3) and immediately following HWA walking (aftereffect). Our overall hypothesis is that walking with the HWA in the (hip flexion and extension) assist mode results in reallocation of cortical motor resources to the knee, ankle, trunk and arm. We also propose that normalizing walking through optimization (activation of latent residual capacity) of previously non-optimized corticospinal motor units with the HWA will produce a short-term (or within-session) aftereffect. We hypothesize that aftereffect will be greater in individuals with less lower extremity use since their stroke. Therefore we will characterize lower extremity use by quantifying the average number of steps each participant takes using an activity monitor.

Background of the device:

The Honda Walking Assist (HWA) System (pictured below) is a robotic device developed by Honda R&D Corporation ®, Japan (https://world.honda.com/Walking-Assist/). It is controlled through software run on a tablet. The device weights 2.7 kgs and has two brushless motors that run on a lithium ion battery with an approximate running time of 60 minutes. It comes in 2 sizes with adjustable frames making it possible to fit a variety of body types/sizes.

It takes approximately 5 minutes to fit the HWA on to the user. It's computer-activated motors use hip angle information to guide assistance delivered through the thigh straps to the legs in time with the walking cycle. The maximum torque delivered is 4 Nm. Wearers have described this level of assistance as "mild" to "moderate". The goal of device use is to promote walking ease by increasing stride length and improving the step symmetry.

Honda began leasing the HWA in Japan in 2015, in January of 2018 they obtained medical device approval in the European Union. Food and Drug administration approval of the HWA in the United States is in process at this time.

Study Objectives:

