- 9. (If applicable) ≥ 90 days post major orthopedic surgery (such as a joint replacement)
- 10. (If applicable) ≥ 6 months post cardiac surgery

[figure not shown]
Exclusion criteria

- Serious cardiac conditions (hospitalized for myocardial infarction or heart surgery within 3 months, congestive heart failure, unstable cardiac arrhythmias, hypertrophic cardiomyopathy, severe aortic stenosis, angina or dyspnea at rest or during activities of daily living)
- 2. Severe arthritis or orthopedic conditions that limit lower extremity range of motion (> 10° or < 90° knee flexion, lacking > 25° hip extension, >15° from neutral plantar flexion.)
- 3. Preexisting neurologic disorders such as Dementia, Multiple Sclerosis, Amyotrophic Lateral Sclerosis, Parkinson's Disease or Ataxia.
- 4. History of lower limb amputation, non-healing ulcers, legal blindness or severe visual impairment

Testing Plan:

Enrolled participants will be pseudo-randomized by drawing from an envelope into either Group A or Group B and scheduled for two testing sessions 1-week ± 3 days apart. Demographic interview, MoCA, Biometrics and StepWatch activity monitor instruction will be conducted on the first testing day for participants in both groups. Group A participants will complete measures in Data Set 2 during the initial

testing session and Data Set 3 during the final testing session. Group B participants will complete measures in Data Set 3 during the initial testing session and Data Set 2 during the final testing session.

[figure not shown]

Each testing sessions will be approximately 2.5 to 3 hours in length. The estimated time for each measure or procedure is indicated in the table below. (data collection forms are attached)

		Time
	Measure or procedure	estimate
	*	(minutes)

	Total time	~2 hours, 5 minutes	
Data Set #3	Kinematic and EMG data collection during walking (see detailed schematic below)	30	
	Set-up of 40 motion capture markers and 16 EMG electrodes on participants body	90	
	Collect StepWatch from participants (Group A)	5	
	Total time	~1 hour 50 min	
Data Set #2	HWA Stair climbing Ascend /Descend test (1st for grp B)	15	
	Activities-Specific Balance Confidence Scale	10	
	Control Stair climbing Ascend/Descent test (1st for grp A)	15	
	Biometrics, EMG and HWA set-up for stairs	30	
	Lower extremity Fugl-Meyer (motor recovery)	10	
	Modified Tardieu Scale (muscle tone)	10	
	Somatosensory testing	5 15	
	Collect StepWatch from participants (Group B)		

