	days of use during their daily routine) Total time	~28 min	
Data Set #1	Instruct participant on use of the StepWatch (send it with them for 3	10	
	Biometrics (height, weight, leg length)	5	
	Montreal Cognitive Assessment (MoCA)	8	
	side affected, assistive devices, Orthoses, handedness)	5	
1	Demographic interview (DOB, sex, date of stroke, type of stroke, body	_	

Kinematic and EMG data collection during walking

Estimated walking distance = 296 meters
Estimated walking time = 12 minutes (calculated based on .4 m/s)
Estimated duration = 30 minutes (including rests, don and doff HWA)

Description of Measures used to characterize participants

- 1. Montreal Cognitive Assessment (MoCA)-a 16-item rapid screen of cognitive abilities designed to detect mild cognitive dysfunction (Nasreddine et al., 2005), 30 points possible.
- Activities-Specific Balance Confidence Scale (ABC)-a 16-item questionnaire with an ordinal scale designed to measure an individual's confidence in their ability to perform daily activities without falling. It has good to excellent reliability and adequate construct validity. (Botner, Miller, & Eng, 2005)
- 3. Fugl-Meyer Assessment of Motor Recovery after Stroke (FMA) The domain for lower extremity motor function will be used (Sections E and F). It has been found to be valid and reliable among individuals with stroke. (Fugl-Meyer, J‰%skˆ, Leyman, Olsson, & Steglind, 1975) 34 points possible.
- 4. Modified Tardieu Scale- A measure of resistance to passive movement at different movement velocities used to quantify the dynamic component of the muscle spasticity. It has been found to be a valid and reliable method of quantifying these features of spasticity in adults with stroke. (Singh, Joshua, Ganeshan, & Suresh, 2011)
- 5. Somatosensation-Three methods of quantifying paretic lower limb somatosensation will be used. Great toe Sharp/dull (# correct/10 trials) assesses the integrity of the anterior Spinothalamic tract. (Kandel, Schwartz, Jessell, Siegelbaum, & Hudspeth, 2000) Great toe up/down testing (# correct/10 trials) assesses the integrity of the dorsal column medial lemniscal system and the higher-level task of discriminating the direction of movement (kinesthesia) (Goble, 2016), Vibration Detection Threshold is a quantitative psychophysical

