- measure of sensitivity thought to reflect A α axon transmission. (Rolke et al., 2006) It will be quantified in seconds and scored using the average of three trials with a 128 Hz tuning fork placed on the skin at the base of the great toenail. (Janz, Bjorkland, Kramer, Oczak, & Borstad, 2018)
- 6. The StepWatch Activity Monitor will be used to characterize participants physical activity based on their daily step counts. Participants will wear StepWatch Activity Monitor on the less affected lower extremity during their daily routines for 8 hours per day for three days. Verbal and written instructions will be provided. The StepWatch is reliable and has been validated to provide the most accurate measurements of physical activity in persons with slow walking, such as may be caused by stroke. (Mudge, Stott, & Walt, 2007) (Mudge & Stott, 2008) Physical activity as measured by daily step count is a potentially large source of variability within the participants that will be important to characterize and understand. In Specific Aims 1 and 2 we will be attempting to quantify a differenced between the control condition and the aftereffect of walking with the HWA. Because we hypothesize that aftereffect will be greater in individuals with less lower extremity use (those who take fewer steps) since their stroke it is important to collect data on this variable.

Description of measures used to quantify effect of HWA on walking

- 7. Kinematic Analysis of Gait will be obtained using a Qualisys 8-camera motion capture system. Sample rate 120 Hz. A modified IOR gait marker set (~40 markers) applied bilaterally. (Cappozzo, Catani, Della Croce, & Leardini, 1995)
- 8. Analysis of muscle activation during gait using 16 Delsys Tringo EMG sensors applied over bilateral LE muscle groups including gluteus maximus (1), quadriceps (3), hamstrings (2), tibialis anterior (1), medial gastrocnemius (1), totaling 8 sensors per lower extremity. Sample rate 2000Hz
- 2 AMTI Force platforms will be used to quantify ground reaction forces (vertical load, horizontal shear, vector patterns, and center of pressure) for both lower limbs during gait. Sample rate 1200Hz.
- 10. Stair Climbing Ascent/Descent test- A timed test of the ability to ascend and descend stairs with our without a rail. For this study a flight of 7 stairs will be used. The means of two trials of ascending and descending will be recorded. (Flansbier et al., 2005)

Withdrawal or removal of participants from the study

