In the case that a participant, for any reason, does not complete the study the following categories will be used to record the occurrence:

- 1. Patient withdraws
- 2. Patient is unable to perform protocol requirements
- 3. Patient demonstrates a change in medical condition
- 4. Patient experiences an adverse event that makes continuation in the protocol unsafe
- 5. PI determines that continuation in the study would not be appropriate
- 6. Other

Study Risks:

This is a study of walking performance therefore risk of falling is present. This risk is similar
to the risk one would undertake while participating in outpatient physical therapy for walking
training following stroke. It will be mitigate by study personnel maintain contact with the
participant during walking, transitions and stair climbing. Participants will be encouraged to

- wear their most comfortable walking shoes and will be walking in a well-lit, open environment.
- 2. While the adhesive materials used in this study are latex free, the risk of skin irritation is present. Skin irritation could arise from the tape used to fix the motion capture markers, the EMG sensors or from the HWA device itself rubbing on the skin. This risk will be discussed with the participants during the process of obtaining informed consent and they will be instructed to inform study personnel if they experience itching or irritation. Participants who demonstrate somatosensory impairment may not feel skin irritation. Those participants will receive a visual skin check in areas of possible irritation midway through the assessments. Adjustments to the size and fitting of the HWA will be conducted to address skin irritation including the possibility of adding additional padding or other measures to reduce irritation.
- The HWA device delivers a maximum 4 Nm of torque to the legs during walking. There is a
 chance that the device could malfunction during use, which could cause a loss of stability or
 balance. To mitigate this risk study personnel will maintain contact with study participants
 during device use.
- 4. There is a possible risk that study participants may develop muscle soreness from the walking or stair climbing they will perform in as part of the assessments. To mitigate this risk participants will be given scheduled rest periods during the protocol and allowed to take additional rest if they choose.

Statistical considerations and Data Management

Study design

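### Step count, the hypothesised predictor of the aftereffect, is recorded only between the two sessions, so no value precedes HWA use and in Group B it follows the aftereffect

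*Combined protocol and SAP*

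**What the plan says.** The section on the background of the question and study rationale states the hypothesis, "We hypothesize that aftereffect will be greater in individuals with less lower extremity use since their stroke", and draws the measurement from it: "Therefore we will characterize lower extremity use by quantifying the average number of steps each participant takes using an activity monitor". Item 6 of the measures used to characterize participants repeats this as the reason for collecting step counts.

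On timing, the Testing Plan says "Demographic interview, MoCA, Biometrics and StepWatch activity monitor instruction will be conducted on the first testing day for participants in both groups". The Data Set 1 row of the schedule reads "Instruct participant on use of the StepWatch (send it with them for 3" (days). Collection is listed under Data Set 3 for Group A and under Data Set 2 for Group B, which is the second session for each. The sessions are one week apart, plus or minus 3 days.

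On wear time, item 6 says "Participants will wear StepWatch Activity Monitor on the less affected lower extremity during their daily routines for 8 hours per day for three days". It does not say which hours, and it calls the result a daily step count.

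The Data analysis plan names paired t-tests and ANOVA and does not mention step count.

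**The concern.** The quantity of interest is leg use between the stroke and the study. A variable meant to predict a response to the device is best measured before any contact with the device, and at the same point for everyone. Here it is measured after the first session in both groups, and that session contains different things in each group. Where the count falls relative to the aftereffect is therefore tied to the order of testing, which the two-group allocation is meant to control in part.

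What is at stake is the relation between step count and aftereffect. If an association appears, a reader could ask whether low use preceded the aftereffect or whether the session influenced walking at home. For Group B the design gives no answer. A pre-exposure count cannot be recovered once a participant has been through session 1.

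The wear-time issue is separate and smaller. If people choose different 8-hour periods, two equally active people can return different counts.

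**Working it through.** **Plan's own figure.** The only sample-size figure is 10 participants for knee flexion (difference 5 degrees, SD 5 degrees, two-sided 5%, power 80%). Taking 5 degrees as the SD of paired differences, the noncentral t distribution gives power 0.748 at n = 9 and 0.803 at n = 10, so 10 is reproduced. It does not involve step count, and nothing below changes it.

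**Which rows belong to which session.** The schedule table is broken in the text, so I checked it by its time totals (minutes):
- Data Set 1: 5 + 8 + 5 + 10 = 28, as stated. It contains StepWatch instruction.
- Data Set 2: 5 + 15 + 10 + 10 + 30 + 15 + 10 + 15 = 110, the stated 1 hour 50. It contains StepWatch collection for Group B and the HWA stair test.
- Data Set 3: 5 + 90 + 30 = 125, the stated 2 hours 5. It contains StepWatch collection for Group A and the walking data.

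**Order of events.**

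| | Session 1 | Between sessions | Session 2 |
|---|---|---|---|
| Group A | Control and HWA stairs | StepWatch, 3 days | Control walking, HWA walking, aftereffect |
| Group B | Control walking, HWA walking, aftereffect | StepWatch, 3 days | Stairs, including HWA |

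Counts taken before any HWA use: 0 of 12. Counts taken after the outcome they should predict: all of Group B, or 12 / 2 = 6 if the groups are equal (an assumption, as no ratio is given).

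**Room between sessions.** The gap is 7 - 3 = 4 to 7 + 3 = 10 days. With session 1 on day 0 and the shortest gap, session 2 is on day 4 and the only three full days between are days 1 to 3. Wear then has to start the day after session 1.

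**Size of the exposure.** Estimated walking is 296 m at 0.4 m/s: 296 / 0.4 = 740 seconds, or 12.3 minutes, across all walking conditions. The stair test is a flight of 7 stairs, with the mean of two trials recorded.

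**Wear time.** Eight hours is 8/24 = 33% of a day. The documents give no waking hours; assuming 12 to 16, it is 8/12 = 67% down to 8/16 = 50% of the waking day. They also do not say how closely an 8-hour count tracks a full-day count, so I put no figure on any loss of correlation.

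**Precision, for context.** No test of the step-count hypothesis is named. If it were a correlation, the value needed for 80% power at two-sided 5% is tanh((1.960 + 0.842) / sqrt(n - 3)): 0.73 at n = 12 and 0.79 at n = 10. The relation is weakly estimable at best, with or without the change.

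**The case against.** The strongest reply is that no harm is shown. The construct is habitual use over the 12 weeks to 1 year since the stroke, and three days just after session 1 sample those months about as well as three days just before it. Order matters only if the session changes walking at home, and the exposure is small. The protocol itself expects the aftereffect to be confined to the session or short-lived. Study Risks, item 4, does say "study participants may develop muscle soreness from the walking or stair climbing", but only as a possible risk, with rests to mitigate it, and it gives no duration and no link to step counts. This stands. A reader might infer that the device or soreness lowers the counts and so biases the moderator; the documents do not support that.

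It can also be said that step count serves to characterize participants, is not among the Specific Aims and is absent from the analysis plan. That limits the weight of the point. It does not remove it, because the protocol attaches a directional hypothesis to the variable.

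On wear time, a fixed 8 hours gives everyone equal observation time and a modest burden, and could rank participants adequately if the hours were common to all. The participant instructions and data forms are not in the text available here and may set the days and hours. The wear-time point is therefore conditional on what they say.

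The order of events is not open to these replies. It follows from the Testing Plan and the schedule.

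**Conclusion.** The point holds as a weakness of design in a secondary question. No step count precedes HWA use. In Group A it falls between the HWA stair test and the aftereffect; in Group B it comes after the aftereffect. Its timing relative to the outcome therefore differs systematically by group.

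Three stronger readings should be resisted. Bias in the counts is possible but not demonstrated. The reversed order applies to Group B only, since Group A's count still precedes its aftereffect. The primary comparison of knee flexion between control and HWA walking, and the sample size of 10 raised to 12, do not depend on step count.

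The timing conclusion rests on the documents alone; only the figure of 6 participants assumes an even split. The unspecified 8-hour window is a lesser matter of definition, and its effect cannot be sized from the documents. Both are worth correcting because the correction is cheap.

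**What to change.** **Timing.** Issue the StepWatch with its written instructions at enrolment, by hand or by mail, at least three full days before session 1, and collect it at session 1 in both groups. Participants are enrolled before they are allocated and scheduled, so the point of handover already exists in the sequence. The edits are to the Testing Plan, the Data Set 1 row and the two collection rows of the schedule, and item 6 of the measures. If the 10-minute instruction leaves Data Set 1 and the 5-minute collection moves into it, the totals become 28 - 10 + 5 = 23, 110 - 5 = 105 and 125 - 5 = 120 minutes.

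The cost is one earlier handover or mailing. The Inclusion criteria already require willingness to wear the monitor for 3 days. The number of wear days, sample size and primary analysis stay as they are. The lag from count to aftereffect will still be longer in Group A, but every count will precede both HWA use and the outcome.

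Moving wear to the last three days before session 2 is not a cure. Every count would still follow HWA use, Group B's would still follow the aftereffect, and at a 4-day gap those are the days straight after session 1.

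**Wear time (secondary).** Either have the monitor worn during all waking hours with on and off times recorded, at slightly more burden, or set the same 8-hour clock window for everyone and call the result an 8-hour count.

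### Group B's marker, EMG and HWA walking session precedes the only scheduled sensory test, so the skin check reserved for participants with sensory impairment has no scheduled trigger there

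*Combined protocol and SAP*

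**What the plan says.** Study Risks, item 2, names the sources of the hazard: "Skin irritation could arise from the tape used to fix the motion capture markers, the EMG sensors", and the HWA itself rubbing on the skin. The general safeguard is that participants are told to report itching or irritation. The protocol then recognises that self-report can fail: "Participants who demonstrate somatosensory impairment may not feel skin irritation". For them it adds a further step: "Those participants will receive a visual skin check in areas of possible irritation midway through the assessments". It does not say how or when these participants are identified.

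The Testing Plan fixes the order of the sessions, which are one week ± 3 days apart. For Group B: "Group B participants will complete measures in Data Set 3 during the initial testing session and Data Set 2 during the final testing session". Group A has the reverse order. The procedures common to both groups on day 1 are: "Demographic interview, MoCA, Biometrics and StepWatch activity monitor instruction will be conducted on the first testing day for participants in both groups". The table of measures lists "Somatosensory testing" once, among the Data Set 2 rows. Neither the day-1 list nor the eligibility criteria contain a sensory item.

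**The concern.** The visual check exists for people whose own reports cannot be relied on, so it works only if someone knows who they are by the time the tape, sensors and device are on. In Group A the sensory test falls at the first visit, before the walking session. In Group B the walking session comes first, and it is the session with both the markers and the full set of EMG sensors. Whether a sensory result exists at that session therefore depends on the envelope draw. At stake is a small matter of participant safety: irritation in someone who may not feel it could go unseen during that session.

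**Working it through.** **1. Where the sensory test sits.** The extracted table is broken, so I checked its placement against the stated block totals (Testing Plan, table of measures; minutes).

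- Data Set 1: 5 + 8 + 5 + 10 = 28. Stated: about 28 min. It matches without a sensory test; a 15-minute test would make it 43.
- Data Set 2: 5 + 15 + 10 + 10 + 30 + 15 + 10 + 15 = 110. Stated: about 1 h 50 min = 110. It matches only with the sensory test; without it the total is 95.
- Data Set 3: 5 + 90 + 30 = 125. Stated: about 2 h 5 min = 125. It matches without a sensory test; with one it would be 140.

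The extract runs two times together (5 and 15) beside the sensory row. I took 15 for the test and 5 for StepWatch collection, since StepWatch collection is 5 minutes in Data Set 3. The reverse assignment gives the same 110. The test is in Data Set 2 only.

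**2. Timing for Group B.** The gap between sessions is 7 − 3 = 4 to 7 + 3 = 10 days. Data Set 3 is first, so the test follows the walking session by 4 to 10 days. In Group A it precedes that session by the same interval.

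**3. Meaning of the check's timing.** The word midway could refer to the middle of a session or to a point in the two-session series. On neither reading does a scheduled test identify an impaired Group B participant before or during the walking session.

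**4. How many.** With equal groups (an assumption), Group B has 12 / 2 = 6 members. The documents give no prevalence of sensory impairment, so the number affected ranges from 0 to about 6. The top of that range needs every member to be impaired and none to be recognised. The sample may also change at the midpoint recalculation.

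**5. Why the timing has to be spelled out.** Simply extending a midway check to everyone would not be enough. Group B's first session is 28 + 90 + 30 = 148 minutes (the 5-minute StepWatch collection in Data Set 3 is for Group A). Its midpoint is 148 / 2 = 74 minutes. If the blocks run in sequence, set-up occupies minutes 28 to 28 + 90 = 118. A literal midpoint check would fall during set-up, before any HWA wear.

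**6. Whether the fix fits.** It needs two checks in the walking session and one in the stair session, each assumed to take 2 to 5 minutes. The stated session length is 150 to 180 minutes.

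| Session | Now | With checks |
|---|---|---|
| Group B, first (walking) | 148 | 152 to 158 |
| Group B, final (stairs) | 110 | 112 to 115 |
| Group A, first (stairs) | 28 + (110 − 5) = 133 | 135 to 138 |
| Group A, final (walking) | 125 | 129 to 135 |

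The longest session keeps at least 180 − 158 = 22 minutes in hand. Counting the 5-minute StepWatch row in it as well gives 157 to 163, still inside the limit.

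**The case against.** The strongest reply is that the protocol never makes the Data Set 2 battery the trigger. The battery is listed among measures that characterise participants, and impairment could be recognised in other ways: the investigators include physical therapists, the day-1 interview covers stroke type and side affected, and 90 minutes of hands-on set-up precede Group B's walking. The Testing Plan figure, the walking schematic, the data collection forms and the consent form are also not available here, and could say who is checked and when. All of this stands. It means the gap is the absence of a scheduled trigger, not a demonstrated failure. A reader might infer that impaired Group B participants will go unchecked; the documents do not support that.

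A reader might also infer that the battery is a poor screen because its tests are at the paretic great toe while sensors and straps sit elsewhere. That does not follow either. The protocol gives the battery no screening role, and presents the toe tests as indicators of pathway integrity, for example: "Great toe Sharp/dull (# correct/10 trials) assesses the integrity of the anterior Spinothalamic tract". Whether a toe result misses sensory loss at the thigh or buttock needs evidence that the documents do not contain.

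Finally, checking everyone at both sessions is broader than a gap in one session of one group. That is true. But it uses a procedure already in the protocol, needs no sensory result and moves no test. The narrower alternative, moving the 15-minute test to Group B's first day, would also fit (148 + 15 = 163 minutes) but costs more time in that session than two checks do.

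**Conclusion.** The point holds as a minor participant-safety improvement. As scheduled, no sensory result exists at Group B's walking session, so the check there depends on informal recognition or on an attachment not seen. The exposure is one session each for 0 to about 6 people. The hazard is skin irritation, and the other safeguards remain: latex-free adhesives, discussion at consent, the instruction to report, and refitting or padding of the HWA. The conclusion rests on the sensory test being in Data Set 2 only, which the block totals support, and on equal groups for the count. A reader might look for an effect on the gait results or the sample size; nothing in the documents links the skin check to any outcome or analysis.

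**What to change.** Replace the skin-check sentence in Study Risks, item 2, with:

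*Every participant, whatever the sensory test result, will have the skin inspected visually at each testing session. In the walking session, tape and sensor sites are inspected after set-up and before the HWA is put on; HWA contact areas are inspected at a rest during HWA walking or, if there is none, directly after the aftereffect walk. In the stair session, the inspection takes place between the two stair tests.*

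The fallback is needed because the walking schematic is not available to confirm a rest during HWA walking. No inspection falls between HWA walking and the aftereffect walk, so the aftereffect is still measured immediately. In Group A the stair inspection comes before the HWA stair test, because its control stair test is first; it therefore covers the EMG sites but not irritation from the HWA on the stairs.

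Cost: three checks per participant, 12 × 3 = 36 at the planned sample, and three more for each participant added at the recalculation. At the assumed 2 to 5 minutes, that is 36 × 2 = 72 to 36 × 5 = 180 minutes of existing staff time over the whole study. Checks made during rests already scheduled would add less. Every session stays within the stated limit: "Each testing sessions will be approximately 2.5 to 3 hours in length".
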